c. Have you felt downhearted and depressed?	 1	 2	 3	 4	 5

7. During the past 4 weeks, how much of the time has our physical health or emotional problems interfered with your social activities (like visiting friends, relatives, etc.)?

All of the time	Most of the time	Some of the time	A little of the time	None of the time
 1	 2	 3	 4	 5

HEALTH LITERACY**Read to subject:**

"This information is on the back of a container of a pint of ice cream."

Questions

	Answer Correct?	
	Yes	No
1. If you eat the entire container, how many calories will you eat? Answer  1,000 is the correct answer		
2. If you are allowed to eat 60 g of carbohydrates as a snack, how much ice cream could you have? Answer Any of the following is correct:  1 cup (or any amount up to 1 cup)  Half the container Note: If patient answers "2 servings," ask "How much ice cream would that be if you were to measure it into a bowl?"		
3. Your doctor advises you to reduce the amount of saturated fat in your diet. You usually have 42 g of saturated fat each day, which includes 1 serving of ice cream. If you stop eating ice cream, how many grams of saturated fat would you be consuming each day? Answer 33 is the only correct answer		
4. If you usually eat 2500 calories in a day, what percentage of your daily value of calories will you be eating if you eat one serving? Answer 10% is the only correct answer		
Pretend that you are allergic to the following substances: Penicillin, peanuts, latex gloves, and bee stings.		
5. Is it safe for you to eat this ice cream? Answer  No		
6. (Ask only if patient responds "no" to question 5): Why not? Answer Because it has peanut oil.		

Total Correct _____

Form Completed by: _____

TRUST

	Strongly Disagree	Disagree	Neutral	Agree	Strongly Agree
1. I doubt that my doctor really cares about me as a person.					
2. My doctor is usually considerate of my needs and puts them first.					
3. I trust my doctor so much I always try to follow his/her advice.					
4. If my doctor tells me something is so, then it must be true.					
5. I sometimes distrust my doctor's opinion and would like a second one.					
6. I trust my doctor's judgments about my medical care.					
7. I feel my doctor does not do everything he/she should for my medical care.					
8. I trust my doctor to put my medical needs above all other considerations when treating my medical problems.					
9. My doctor is a real expert in taking care of medical problems like mine.					
10. I trust my doctor to tell me if a mistake was made about my treatment.					
11. I sometimes worry that my doctor may not keep the information we discuss totally private.					

PERCEIVED DISCRIMINATION

Everyday Discrimination Scale (Short Version)

In your day-to-day life how often have any of the following things happened to you?

	Almost everyday	At least once a week	A few times a month	A few times a year	Less than once a year	Never
1. You are treated with less courtesy or respect than other people.						
2. You receive poorer service than other people at restaurants or stores.						
3. People act as if they think you are not smart.						
4. People act as if they are afraid of you.						
5. You are threatened or harassed.						

Follow-up Question (Asked only of those answering "A few times a year" or more frequently to at least one question.): What do you think is the main reason for these experiences? (check more than one if volunteered).

Recommended options:

1. Your Ancestry or National Origins
2. Your Gender
3. Your Race
4. Your Age
5. Your Religion
6. Your Height
7. Your Weight
8. Some other Aspect of Your Physical Appearance
9. Your Sexual Orientation
10. Your Education or Income Level

Other possible categories to consider:

1. A physical disability
2. Your shade of skin color
3. Your tribe
4. Other (specify): _____

Form Completed by: _____

Visit: **BL**

Date of Visit: ____ / ____ / ____

Subject ID: ____

ENGLISH PROFICIENCY

	Poor	Fair	Good	Excellent
1. How well do you speak English				
2. How well do you write English				
3. How well do you read English				

Form Completed by: _____

Visit: **BL** **12M** Date: ____ / ____ / ____ Time: ____ : ____ AM PM Study ID#: _____**ECHOCARDIOGRAM**

Dimensions	Value
LV End Dias. Internal Dimension (cm)	
LV End Sys. Internal Dimension (cm)	
LVOT Dimension (cm)	
Left Atrial Diameter (cm)	
Inferior Vena Cava (cm)	
IVC Collapse >50%	 Yes  No

Volume / Area	Value
LV End-Diastolic Volume (ml) (via Simpson's, Devereux and Bi-Plane)	
LV End-Systolic Volume (ml) (via Simpson's, Devereux and Bi-Plane)	
LV Stroke Volume (ml)	
LV Ejection Fraction (%)	
Cardiac Output (l/min)	
LA Volume (ml) (via Bi-Plane)	
RA Volume (ml) (via Bi-Plane)	
RV EDA (cm ²)	
RV ESA (cm ²)	
RV FAC (%)	

Mass / Thickness	Value
LV Myocardial Mass End Diastole (via Simpson's, Devereux and Bi-Plane)	
LV Myocardial Mass End Systole (via Simpson's, Devereux and Bi-Plane)	
Intraventricular Septal Thickness (via 2D)	
Posterior Wall Thickness (via 2D)	
RV Wall Thickness (via 2D)	
LV Wall Thickness at Mid-Cavity (via 2D)	

Cardiac Valves				
Regurgitation				
	Normal	Mild	Moderate	Severe
Aortic				
Mitral				
Pulmonic				
Tricuspid				

Wall motion assessment
 Normal
 Global hypokinesis
 Regional wall motion abnormalities
Abnormal segments:

Hemodynamic Variables	Value
AV Velocity Time Integral (cm) (area under curve traced in CW)	
Isovolumetric Relaxation Time (sec - measured from LVOT in PW)	
Isovolumetric Contraction Time (sec - measured from LVOT in PW)	
Aortic Ejection Time (sec)	
LVPEP (sec)	
MV Peak E Wave Velocity (cm/sec)	
MV Peak A Wave Velocity (cm/sec)	
Mitral E/A Ratio	
Mitral Deceleration Time (sec)	
Mitral Inflow Deceleration Slope	
Mitral Wave A Duration (sec)	
TV Regurgitant Jet Velocity (cm/sec)	
TV Max Pressure Gradient (mmHg)	
TV Excursion – TAPSE (cm)	

Tissue Doppler	Value
MV Lateral Velocity (cm/sec)	
MV Septal Velocity (cm/sec)	
TV Annular Velocity (cm/sec)	

Strain	Value
Global Longitudinal Strain	
Average Apical Segment Strain	
Average Mid-Segment Strain	
Average Basal Segment Strain	

Incidental Findings

Form Completed by: _____ Investigator's Signature: _____

99mTc-PYP CARDIAC AMYLOID SCINTIGRAPHY Imaging Sheet**Vital signs**Time collected: ____ : ____ (24-hour clock)
(To be collected before dosing)Position: Sitting Supine

Systolic blood pressure: ____ mmHg

Diastolic blood pressure: ____ mmHg

Heart rate: ____ bpm

SPECT/CT Imaging Details (if applicable)Was SPECT/CT imaging performed? Yes

No

Imaging start time: ____ : ____ (24-hour clock)

Imaging stop time: ____ : ____ (24-hour clock)

Time between injection and acquisition:
____ : ____ (hh:mm)

Imaging protocol:

 SPECT Gated SPECTType of scan: **CTAC scan**Applied to: **Rest**Tube voltage (kV): **120**

Tube current (mAs): _____

Radiation dose (DLP): _____

Injection Details **99mTc-PYP** **99mTc-HMDP**

Injectate lot number: _____

Assay date: ____ / ____ / ____ (mm/dd/yyyy)

Assay time: ____ : ____ (24-hour clock)

Assay activity: _____ mCi

Injection time: ____ : ____ (24-hour clock)

Injection site:

 Antecubital Hand Other, specify: _____

Residual time: ____ : ____ (24-hour clock)

Residual activity: _____ mCi

Total injected activity: _____ mCi

Planar Imaging Details

Imaging start time: ____ : ____ (24-hour clock)

Imaging stop time: ____ : ____ (24-hour clock)

Time between injection and acquisition: (ideally 3 hrs)
____ : ____ (hh:mm)Image duration: _____ counts
(750,000 minimum counts)**Adverse Reactions (AR)**Any AR to radiotracer injection? Yes No

If 'Yes', please check all that apply:

 Flushing Itching Hypotension Skin rash Fever Chest pain Chills Palpitations Nausea Tachycardia Vomiting Shortness of breath Dizziness Other (specify): _____**Difficulties with Scan**

Please note any difficulties in obtaining the scan. For example, difficulty positioning the participant, participant motion, etc. and any action taken to correct it.

Form Completed by: _____

CARDIAC AMYLOID SCINTIGRAPHY Findings Sheet**Nuclear Findings****Planar myocardial radiotracer uptake pattern:**

 Absent	 Diffuse
 Focal	 Focal on diffuse

Semi-quantitative visual grading of radiotracer uptake – based on “Planar” images:

- Grade 0: no uptake and normal bone uptake
- Grade 1: uptake less than rib uptake
- Grade 2: uptake equal to rib uptake
- Grade 3: uptake greater than rib uptake with mild/absent rib uptake

Was SPECT imaging performed? Yes No

If 'Yes':

Semi-quantitative visual grading of radiotracer uptake – based on “Planar” and “SPECT” images:

- Grade 0: no uptake and normal bone uptake
- Grade 1: uptake less than rib uptake
- Grade 2: uptake equal to rib uptake
- Grade 3: uptake greater than rib uptake with mild/absent rib uptake

Quantitative interpretation of radiotracer uptake:

H/CL ratio: ____ . ____

If SPECT or SPECT/CT done, blood pool activity:

- Absent
- Minimal
- Significant

Technical Findings**Study difficulties:**

- None
- Participant motion
- High background
- Inadequate count density
- Dose infiltration
- Delay in imaging
- Poor labeling
- Other, specify: _____

Artifact Findings**Incidental Findings***(Bone findings, hot spots, pleural or pericardial effusion, etc.)***Comments****Conclusion****Overall interpretation:**

- Not suggestive of ATTR
- Strongly suggestive of ATTR
- Equivocal for ATTR / Possible early ATTR

Study quality:

- Uninterpretable
- Poor
- Fair
- Good
- Excellent

ON-SITE FOLLOW-UP

1. Was the study visit conducted? Yes No

a. If no, did the patient drop out of the study? Yes No

If yes, date of drop out: ____ / ____ / _____

If yes, provide reason subject dropped out, and **go to #2**:

b. If no, did the subject die? Yes No

If yes, date of death: ____ / ____ / _____

Is death related to study participation? Definitely Possibly Not related

If yes, provide description/narrative, and **go to #2**:

c. If no, provide reason subject missed visit:

2. Has the patient been hospitalized? Yes No

If yes, number of hospitalizations: ____

If yes,

Reason	Causality			Hospital	Date of admission	Date of discharge
	HF	CVA	Other CVD			
1						
2						
3						
4						
5						

3. Was the patient seen in the ER? Yes No

If yes, number of ER visits: ____

If yes,

Reason	Causality			Hospital	Date of admission	Date of discharge
	HF	CVA	Other CVD			
1						
2						
3						
4						
5						

4. Has the patient had any ambulatory procedures/interventions (no overnight stay) Yes No

If yes, number of procedures ____

If yes,

Visit: **6M** **12M**

Date of Visit: ____ / ____ / _____

Study ID#: _____

Reason	Causality			Hospital	Date of procedure
	HF	CVA	Other CVD		
1					____ / ____ / ____
2					____ / ____ / ____
3					____ / ____ / ____
4					____ / ____ / ____
5					____ / ____ / ____

5. Has the patient been infected with COVID-19? Yes No

If yes, date of COVID-19 diagnosis: ____ / ____ / _____

Visit: **6M** **12M**

Date of Visit: ____ / ____ / _____

Study ID#: _____

Form Completed by: _____ Investigator's Signature: _____

PHONE CALL FOLLOW-UP1. Was any data collected? Yes NoIf yes, Phone Chart review Phone and chart review

If no, reason: _____

If no, deceased? Yes No

If yes, date of death: ____ / ____ / _____

Is death related to study participation? Definitely Possibly Not related

Description / Narrative:

--

2. Has the patient been hospitalized? Yes No

If yes, number of hospitalizations: ____

If yes,

Reason	Causality			Hospital	Date of admission	Date of discharge
	HF	CVA	Other CVD			
1						
2						
3						
4						
5						

3. Was the patient seen in the ER? Yes No

If yes, number of ER visits: ____

If yes,

Reason	Causality			Hospital	Date of admission	Date of discharge
	HF	CVA	Other CVD			
1						
2						
3						
4						
5						

4. Has the patient had any ambulatory procedures/interventions (no overnight stay) Yes No

If yes, number of procedures ____

If yes,

Reason	Causality			Hospital	Date of procedure
	HF	CVA	Other CVD		
1					
2					
3					
4					
5					

5. Has the patient been infected with COVID-19? Yes No

If yes, date of COVID-19 diagnosis: ____ / ____ / _____

SERIOUS ADVERSE EVENT**Part A. Event Type**

1. Type of adverse experience (check all that apply)

 Hospitalization or prolongation of hospitalization

(specify reason: _____)

 Persistent or significant disability. Date: ____ / ____ / ____ Life threatening. Date: ____ / ____ / ____ ER / Urgent Care Visit (specify reason: _____) Important medical event that represents significant risk or harm to the participant and may require medical or surgical intervention to prevent one of the other outcomes (e.g. hospitalization, persistent disability, death). Date: ____ / ____ / ____

(Specify event: _____)

 Death: **SKIP TO PART C****Part B. Nonfatal Events**

2. Was the participant hospitalized overnight for this experience?

 No (**Skip to Question 3**) Yes, complete the following:

Hospital Name: _____

Street Address: _____

City: _____

State: _____

Zip Code: _____

Date participant entered the hospital: ____ / ____ / ____ Check here if unknown: Date participant left the hospital: ____ / ____ / ____ Check here if unknown/ongoing:

3. Did the participant receive treatment for the experience in an ER or Urgent Care without being hospitalized overnight?

 No (**Skip to Question 4**) Yes, Complete the following:

Institution: _____

Street Address: _____

City: _____

State: _____

Zip Code: _____

Date of visit ____ / ____ / ____ Check here if unknown:

Form Completed by: _____ Investigator's Signature: _____

Visit: **ALL**

Date of Visit: ____ / ____ / _____

Subject ID: _____

4. Describe this adverse experience. What was the condition or symptoms the participant was having? What tests or procedures were performed?

5. Describe any relevant history, including pre-existing conditions, medications, etc. Skip to Part D when finished.

Form Completed by: _____ Investigator's Signature: _____

Part C. Fatal Events

6. Date of death: ____ / ____ / ____ Check here if unknown:

7. Where did the death occur?

In the hospital
 In the ER
 Out of hospital (includes DOA, Rehab. Center, Hospice or Nursing Home; **Skip to 10**)
 Unknown (**Skip to 10**)

8. Hospital or ER Name: _____

Street Address: _____

City: _____

State: _____

Zip Code: _____

Date participant entered the hospital or ER: ____ / ____ / ____ Check here if unknown:

9. **For out of hospital death cases, including deaths that occur in an ER, skip to 10.**
For hospital deaths only: describe the reason for the hospitalization, the symptoms the participant was having, and conditions treated. Also, any events, procedures, or tests that occurred before the participant died. (Skip to Part D when finished). Hospital records may be requested by the Central Study Coordinator.

Form Completed by: _____ Investigator's Signature: _____

10. For out-of hospital death (including those that occur in the ER): list the location (including city and state), social setting, and type and duration of symptoms. Specific symptoms of interest include: angina; pain or discomfort in the chest, left arm, shoulder or jaw; increased fatigue or tiredness; shortness of breath; dizziness; palpitations; paralysis; loss of speech.

Be as specific as possible when reporting information such as the precise location of death, when the patient was last seen alive, who last saw the patient alive, and location of those final sightings in relation to the site where the participant died. The Central Study Coordinator may request any information about the patient's treatment during the last six months of life. If you need more space, write on the back of this form.

Part D. SAE Summary

11. Outcomes: Indicate any of the specific following conditions that occurred as part of this experience (mark all that apply).

- Arrhythmia, atrial fibrillation or flutter
- Heart Attack
- Stroke or TIA
- New or worsening Heart Failure/Heart Failure Exacerbation
- Chest pain (hospitalized only)
- Kidney Failure / Dialysis
- GI Bleeding
- Infection
- Arrhythmia, Ventricular
- Amputation of part of leg, including toes, because of poor circulation/gangrene
- Other problems with heart, brain or circulation (specify: _____)

Form Completed by: _____ Investigator's Signature: _____

Visit: **ALL** Date of Visit: ____ / ____ / ____

Subject ID: ____

12. Was this event caused or worsened by enrollment in the study or any of its procedures?

- No
- Possibly
- Definitely

If possible or definitely, why?

13. Investigator Signature (Indicate when reviewed and approved by Clinic PI)

Signature: _____ Date: ____ / ____ / ____

Form Completed by: _____ Investigator's Signature: _____

Adverse Events Log

Protocol: _____	IRB #: _____
Principal Investigator: _____	Site: _____
Subject ID #: _____	

Adverse Event (Please use medical terminology)	Serious Adverse Event	Date Site Became Aware	Start Date	End Date - OR - Continuing	Severity (Grade)	Relatedness to Study Participation	Outcome	Report to External Entities (If applicable)	PI Initial & Date
	 No  Yes * <small>* Complete SAE Form</small>	 /  /20 <small>(mm/dd/yyyy)</small>	 /  /20 <small>(mm/dd/yyyy)</small>	 /  /20 <small>(mm/dd/yyyy)</small>  Continuing	 1 - Mild  2 - Moderate  3 - Severe  4 - Life-threatening  5 - Death	 Definitely  Probably  Possibly  Unlikely  Not Related  Unknown	 Recovered/Resolved  Recovered/Resolved with Sequelae  Not Recovered/Not Resolved  Fatal  Other (specify): _____	<small>IRB</small>  Yes  No <small>FDA</small>  Yes  No <small>Sponsor</small>  Yes  No	
	 No  Yes * <small>* Complete SAE Form</small>	 /  /20 <small>(mm/dd/yyyy)</small>	 /  /20 <small>(mm/dd/yyyy)</small>	 /  /20 <small>(mm/dd/yyyy)</small>  Continuing	 1 - Mild  2 - Moderate  3 - Severe  4 - Life-threatening  5 - Death	 Definitely  Probably  Possibly  Unlikely  Not Related  Unknown	 Recovered/Resolved  Recovered/Resolved with Sequelae  Not Recovered/Not Resolved  Fatal  Other (specify): _____	<small>IRB</small>  Yes  No <small>FDA</small>  Yes  No <small>Sponsor</small>  Yes  No	
	 No  Yes * <small>* Complete SAE Form</small>	 /  /20 <small>(mm/dd/yyyy)</small>	 /  /20 <small>(mm/dd/yyyy)</small>	 /  /20 <small>(mm/dd/yyyy)</small>  Continuing	 1 - Mild  2 - Moderate  3 - Severe  4 - Life-threatening  5 - Death	 Definitely  Probably  Possibly  Unlikely  Not Related  Unknown	 Recovered/Resolved  Recovered/Resolved with Sequelae  Not Recovered/Not Resolved  Fatal  Other (specify): _____	<small>IRB</small>  Yes  No <small>FDA</small>  Yes  No <small>Sponsor</small>  Yes  No

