Six-Minute Walk Test		X	X	X
Short Physical Performance Battery		X	X	X
QoL Questionnaires		X	X	X
Health Literacy Questionnaire		X		
Echocardiogram		X		X
^{99m} Tc-PYP Scintigraphy**		X		
Phone Call Follow-Up [¶]			X	X

* Follow-up visits are to be conducted on subjects who test positive to the Cardiac Amyloid Scintigraphy scan and/or are carrier of the V122I mutation. Window for the 6-month visit is ±2 weeks and for the 12-month visit is ±4 weeks.

† Height measured only at baseline visit. Subjects with weight >350 lb will not participate in the study.

‡ Includes BNP, NT-proBNP, galectin-3, troponin I and T.

§ Includes Vitamin A and RBP4 in on site spot urine.

¶ For participants with no TTR CA, a phone call follow-up will be conducted instead.

**In the event that PYP is unavailable due to supply shortage, the investigator has the option of using HDP until PYP becomes available again to ensure study continuation per FDA.

For every study visit, a checklist will be used to help ensure completion of all the study procedures. The checklist is also a guide that suggests the order in which the assessments should be performed (See [Appendix 3](#)).

TABLE OF CONTENTS

STUDY SYNOPSIS.....	2
LIST OF ABBREVIATIONS AND DEFINITIONS OF TERMS.....	9
1. INTRODUCTION	10
1.1 Background and Rationale	10
1.1.1 Transthyretin Biology	10
1.1.2 Transthyretin-mediated amyloidosis definition	10
1.1.3 Pathogenesis and Outcome.....	11
1.1.4 ATTR-CM and Heart Failure	11
1.2 ATTR-CM Population Burden.....	13
1.2.1 ATTR amyloid is an under-recognized cause of heart failure	13
1.2.2 Are Hispanics affected by TTR-CA?	14
1.2.3 TTR-CA from mutant protein has more severe phenotype than wild type	14
1.3 Natural History of Transthyretin Cardiac Amyloidosis	15
1.3.1 Clinical Characteristics and Outcome in ATTR-CA in TRACS	15
1.3.2 Predictors of Mortality	16
1.4 Therapeutic Options.....	17
1.4.1 Novel Therapies Require Early Identification of Affected Individuals	17
1.4.2 Tc-PYP & Tc-HMDP can detect TTR-CA without the need for an amyloid biopsy	
18	
1.4.3 Myocardial retention of Tc99-PYP is prognostic in TTR-CA	18

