Hypothesis 4. Progression of disease: Markers of disease progression are lacking in ATTR CA. We hypothesize that attainment of a hierarchical composite endpoint at 1-year of death, heart failure hospitalization, and 30% decline in 6-minute hall walk will be higher in ATTRm vs. ATTRwt CA. In addition, we will explore the capacity of specific markers to assess disease progression including: (1) established circulating biomarkers such as troponin I/T, NT-proBNP, BNP and Galectin-3, (2) novel biomarkers such as RBP4 and TTR concentration, (3) ECG, and

echocardiographic measures including longitudinal strain and MCF, (4) functional capacity by 6-minute hall walk and SPPB, and (5) QOL. Our preliminary data and published work⁹ suggests reduced median survival for ATTRm Val122Ile CA (25 months) vs ATTRwt (43 months) in different race cohorts. We hypothesize that we will observe reduced survival and greater functional decline in ATTR Val122Ile vs ATTRwt within race cohorts.

Hypothesis 5. Performance of risk calculator: Our point-of-care risk calculation utilizing RBP4 and TTR concentration with echocardiographic and ECG determined parameters will be tested in this cohort. We will re-derive the prediction model based upon clinical variables noted above. We anticipate showing a similar degree of accuracy (ROC AUC > 0.95) for identification of cases with ATTR vs. controls

Specific Aim 2: To demonstrate that circulating RBP4 concentration is integral to TTR tetramer stability, which in turn determines the clinical characteristics of ATTR CA. We will measure TTR tetramer stability and RBP4 concentration in serum and urine collected in Aim 1. The overall hypotheses of this Aim are that measurements of TTR kinetic stability, RBP4 and TTR concentration will differentiate patients with ATTR CA vs. non-amyloid HF controls and associate with disease progression and outcomes. Specific hypotheses are as follows:

Hypothesis 1: TTR kinetic stability and RBP4 concentration: We hypothesize that at baseline, TTR kinetic stability will be lower in ATTR CA vs. non-amyloid HFpEF, and that stability will be inversely proportional to plasma RBP4 concentration. We further hypothesize that TTR kinetic stability will be lower for ATTRm vs. ATTRwt.

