APPENDIX 4 CASE REPORT FORMS

Visit: **SCR**

Date of Visit: ____ / ____ / ____

Subject ID: ____

SCHEDULE OF ACTIVITIES – SCREENING

Order	Activity	Done	Not Done	Notes
1	Informed consent			
2	Inclusion and Exclusion Criteria			
3	Demographics and Contact Information			

Form Completed by: _____

SCHEDULE OF ACTIVITIES – BASELINE

Order	Activity	Done	Not Done	Notes
1	Baseline history			
2	Medications			
3	Height and Weight			
4	Vital signs			
5	Clinical examination			
6	Electrocardiogram			
7	Short physical performance battery			
8	Six-minute walk test			
9	Echocardiogram			
10	IV catheter placement			
11	Blood/urine samples collection			
	a. Basic metabolic panel			
	b. Hepatic function panel			
	c. NT-proBNP, BNP and Galectin-3			
	d. Troponin I and T			
	e. Vitamin A / RBP4 in plasma			
	f. Vitamin A / RBP4 in urine			
	g. Prealbumin			
	h. TTR kinetic stability			
	i. TTR gene sequencing			
	j. Ancestry analysis			
12	Injection of radioisotope (^{99m} Tc-PYP or ^{99m} Tc-HMDP)			
13	QoL questionnaires			
14	Health Literacy Questionnaire			
15	Cardiac Amyloid Scintigraphy scan			

Form Completed by: _____

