SCHEDULE OF ACTIVITIES – MONTH 6

Order	Activity	Done	Not Done	Notes
1	Weight			
2	Vital signs			
3	Medications			
4	Clinical examination			
5	Adverse events review			
6	Electrocardiogram			
7	Blood/urine samples collection			
	a. Basic metabolic panel			
	b. Hepatic function panel			
	c. NT-proBNP, BNP and Galectin-3			
	d. Troponin I and T			
	e. Vitamin A / RBP4 in plasma			
	f. Vitamin A / RBP4 in urine			
	g. Prealbumin			
8	Short physical performance battery			
9	Six-minute walk test			
10	QoL questionnaires			

Form Completed by: _____

SCHEDULE OF ACTIVITIES – MONTH 12

Order	Activity	Done	Not Done	Notes
1	Weight			
2	Vital signs			
3	Medications			
4	Clinical examination			
5	Adverse events review			
6	Electrocardiogram			
7	Blood/urine samples collection			
	a. Basic metabolic panel			
	b. Hepatic function panel			
	c. NT-proBNP, BNP and Galectin-3			
	d. Troponin I and T			
	e. Vitamin A / RBP4 in plasma			
	f. Vitamin A / RBP4 in urine			
	g. Prealbumin			
	h. TTR kinetic stability			

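### The visit checklists place blood and urine collection after the SPPB and six-minute walk at baseline but before them at months 6 and 12, so change from baseline in the blood markers compares samples taken under different conditions.

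*Combined protocol and SAP*

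**What the plan says.** The text under the synopsis Schedule of Activities says of the visit checklists: "The checklist is also a guide that suggests the order in which the assessments should be performed". It points to Appendix 3, but the checklists are in Appendix 4.

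- **Baseline checklist:** "Short physical performance battery" is item 7 and "Six-minute walk test" item 8. The echocardiogram is item 9, "IV catheter placement" item 10, "Blood/urine samples collection" item 11 and the radioisotope injection item 12.
- **"SCHEDULE OF ACTIVITIES – MONTH 6":** blood and urine are item 7, SPPB item 8 and walk item 9. There is no echocardiogram or injection.
- **"SCHEDULE OF ACTIVITIES – MONTH 12":** blood and urine are item 7, SPPB item 8, walk item 9 and echocardiogram item 11. There is no injection.

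The draw includes BNP, NT-proBNP, galectin-3, troponin I and T, RBP4, vitamin A and prealbumin at all three visits, and TTR kinetic stability at baseline and month 12. Section 2.1.5.4 (Laboratory Analysis) and Section 2.1.5.7 (Functional Capacity) give no rest period and no timing of sampling relative to the walk.

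Section 2.1.6, Aim 1 Hypothesis 4, plans to explore markers of progression, including "established circulating biomarkers such as troponin I/T, NT-proBNP, BNP and Galectin-3" and RBP4. Section 2.1.7 gives a power statement for Aim 2 worded as a mean change difference in TTR stability.

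**The concern.** A change-from-baseline measure is interpretable only if the two samples are taken under like conditions. A site that follows the suggested order draws baseline blood after two performance tests and follow-up blood before them. The participants are heart failure patients aged 60 or over, and the walk script in Appendix 4 itself warns them to expect breathlessness or exhaustion. Any residual effect of that exertion would sit in the baseline value alone and would enter each participant's change at months 6 and 12. What is at stake is the exploratory work on which markers track progression, and any change in TTR stability drawn from the same tubes.

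**Working it through.** **Step 1. The order columns side by side** (Appendix 4 checklists):

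| Visit | SPPB | Walk | Echocardiogram | Blood/urine |
|---|---|---|---|---|
| Baseline | 7 | 8 | 9 | 11 |
| Month 6 | 8 | 9 | none | 7 |
| Month 12 | 8 | 9 | 11 | 7 |

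Blood follows both performance tests at baseline and precedes both at each follow-up visit. The reversal is in the text.

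**Step 2. Does anything else in the protocol remove it?** No. The schedule tables list what is done at each visit, not in what sequence. The laboratory and functional capacity sections are silent on sequence and rest.

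**Step 3. Size, by assumption only.** The documents state no exertion effect. Let e be the proportional rise in the baseline value due to sampling after the walk, and R the true follow-up/baseline ratio. The observed ratio is R / (1 + e). With no true change (R = 1), the apparent change is 1/(1 + e) - 1:

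- e = 0%: 0%
- e = 5%: 1/1.05 - 1 = -4.8%
- e = 10%: 1/1.10 - 1 = -9.1%
- e = 20%: 1/1.20 - 1 = -16.7%

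A true 10% rise would read as 1.10/1.05 = 1.048 (+4.8%) at e = 5%, and as 1.10/1.20 = 0.917 (-8.3%) at e = 20%. If sampling after the walk lowered a marker, the shift would go the other way. One value of e need not fit all the analytes.

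**Step 4. The ATTRm v ATTRwt contrast.** With a common e, the ratio of ratios is [Rm/(1 + e)] / [Rwt/(1 + e)] = Rm/Rwt, so the offset cancels. A shared additive offset likewise cancels in a difference of changes. With different effects, the contrast is multiplied by (1 + e_wt)/(1 + e_m), which equals 1 only when the two effects are equal.

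**Step 5. Which results are touched?**

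- Affected: within-group change from baseline to month 6 or 12 in any analyte from this draw.
- Not affected: prevalence; the composite of death, heart failure hospitalization and walk decline; baseline cross-sectional comparisons, since all baseline samples share one suggested order; and month 6 to 12 change, since both draws precede the walk.

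**Step 6. How many participants?** Section 2.1.7 gives 80-160 ATTR CA subjects in one place and 80-120 in another. V122I carriers also return for follow-up visits, so the number with serial samples is not fixed by the documents.

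**The case against.** The strongest reply has four parts.

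1. **The order is suggested, not required.** The documents do not show that baseline blood is in fact drawn after the walk. That stands. It also means that practice may vary by site, and the checklists have Done/Not Done boxes but no draw time, so the order used may not be recoverable.
2. **Post-exertion against resting is too stark.** A full echocardiogram and catheter placement come between the walk and the baseline draw, for an unstated interval. The walk is self-paced and allows stops. The follow-up draw has no stated rest either. That stands, and it is why zero belongs in the assumed range.
3. **No specific analysis is shown to be biased.** Section 2.1.8 defines no change-from-baseline analysis of the cardiac biomarkers; they appear there only as variables to be explored in the Cox model. This stands in part: the stated use in Section 2.1.6 is still to assess progression, and the markers are scheduled at three visits for participants who return for follow-up.
4. **Moving the baseline draw forward has a cost.** The baseline catheter comes just before blood collection and the isotope injection. Placing it first means walking with it in or a second venipuncture. A mid-study switch would also mix two sampling conditions in the baseline case-control comparisons. That stands, and it decides which visit should change.

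A reader might infer that true worsening is being understated, or that the ATTRm v ATTRwt contrast is distorted. The documents support neither. The first needs an exertion effect of known direction. The second needs an effect that differs between genotypes. Nor do they say whether exertion alters the TTR stability assay.

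**Conclusion.** The inconsistency is real and nothing in the documents explains it. Following the protocol's only guidance on order yields unlike samples for change from baseline. The consequence is limited to exploratory within-group change and, through the same draw, change in TTR stability. Under an assumed 0 to 20% rise in the baseline value, the shift in apparent change is 0 to -17%; both the range and its sign are assumptions. The main conclusions of the study do not depend on this. It is worth correcting because the correction is nearly free and the problem is hard to repair once samples are collected without draw times.

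**What to change.** Use one order relative to the SPPB and walk at every visit. The simplest way is to move blood and urine collection on the follow-up checklists to after the walk and, at month 12, after the echocardiogram as well. This matches baseline samples already taken and leaves the baseline catheter and injection sequence alone.

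- Add a draw-time field at every visit.
- Month 6 has no echocardiogram, so state a walk-to-draw interval there similar to that at baseline.
- Flag participants whose visits used different orders.
- As a sensitivity analysis, report month 6 to 12 change, or repeat the change-from-baseline analysis without the flagged participants. After the switch, month 6 to 12 change is like-for-like only where both follow-up draws were in the same order, so restrict it accordingly.

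**Cost:** a small change to follow-up visit flow, one extra field, and a flag for follow-up samples already drawn before the walk. That flag may be imperfect for past visits, because no draw time appears on the checklists.
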